1 BACKGROUND/SCIENTIFIC RATIONALE

Previous studies evaluating the effect of needle priming with heparin for liver biopsies have shown that heparinized needles improved histologic yield and tissue adequacy.^{1,2} With regards to pancreatic lesions, two retrospective studies showed that needle priming with heparin during EUS fine needle aspiration (FNA) of pancreatic solid lesions was not superior to conventional methods on tissue yield, sample adequacy, bloodiness, and number of passes.^{3,4} In contrast, a recent crossover RCT from Taiwan, found that among 50 patients with solid pancreatic masses, EUS-guided biopsy with a heparinized needle obtained longer white tissues with less blood contamination than with conventional EUS-FNB.⁵ However, the study measured tissue length with macroscopic on-site evaluation (MOSE), which is prone to investigator and measurement bias. In addition, the investigators used the same needle for each patient at the time of the crossover to the 2nd intervention, which introduces the possibility of needle contamination in those who were randomized to undergo sampling with the heparinized needle first. Finally, EUS sampling was performed using an old needle design not commercially available in the United States (20-gauge EchoTip ProCore needle) and by a single endoscopist, which limits the external validity of the results. Although these results are important, they cannot be generalizable and need to be confirmed in high-quality RCTs.

When sampling pancreatic masses with EUS-FNN, multiple passes are often performed to improve diagnostic accuracy and reduce false negative results. However, the impact of successive EUS-FNB passes on tissue quality is unknown. This may have a direct impact on specimens collected for purposes other than diagnostic histopathology, since the endoscopist typically reserves the first FNB passes for clinical histopathology and may collect the last passes for personalized medicine applications (e.g. next generation DNA or RNA sequencing).⁶ However, it is unclear whether successive passes will have the same tissue quality, as needles may progressively become contaminated with blood.

In this proposal, we aim to provide guidance on how tissue quality is affected by successive EUS-FNB passes, and whether this may be mitigated by heparinizing the FNB needle. The results of this study will provide guidance to endoscopists regarding whether heparin can improve tissue quality when sampling solid pancreatic masses, the number of passes that is needed to obtain adequate tissue, and how to divide up the number of FNB passes for multiple applications. For pancreatic cancer patients, this is highly relevant, as precision platforms that may impact their care such as Know Your Tumor⁷, and clinical trials such as Precision Promise⁸, require adequate tumor tissue quality for eligibility. This will be a pilot study, as there have been no studies specifically looking at the effects of heparin priming and fine needle biopsy on tissue yield and blood contamination of pancreatic masses.

2 OBJECTIVES

Primary objective:

- *Determine whether heparin priming of FNB needle improves tissue quality as compared to standard FNB for EUS-tissue acquisition of pancreatic masses.*

Secondary objectives:

- *Determine whether heparin priming of FNB needle improves cellularity.*
- *Determine whether heparin priming of FNB needle reduces blood contamination.*
- *Determine whether heparin priming of FNB needle improves histologic yield.*
- *Determine whether increasing number of FNB passes affects tissue quality, block contamination, and histologic yield.*
- *Determine the incremental diagnostic yield with a second or third FNB pass as compared to a single FNB pass.*

Hypothesis:

We hypothesize that the tissue quality of EUS-FNB specimens of pancreatic masses decreases with increasing pass number due to blood contamination. This blood contamination can be ameliorated with priming of the needle with an anticoagulant such as heparin, resulting in improved tissue quality of EUS-FNB of pancreatic masses.

Anticipated Results

- *We anticipate that histologic yield will decrease and blood contamination will increase with increasing number of FNB passes*
- *We anticipate that the intervention of heparin priming of the biopsy needle will decrease blood contamination and increase histologic yield.*

Trial design

- Single center, double-blind, superiority, parallel-group, 1:1 ratio, randomized controlled trial

3 EXPECTED RISKS/BENEFITS

There are no immediate benefits to participating in this study. Of note, IF a diagnosis of malignancy is made on the tissue obtained for research by a blinded clinical pathologist AND the diagnosis was not made on the passes obtained for clinical purposes, the patient will be notified. In this event, either the PI or one of the co-investigators (all of which are practicing physicians) will reach out to the patient personally to inform them of the discrepancy and make arrangements for the research block to be submitted to pathology for further evaluation. Furthermore, the patient's physician will be notified, and the patient will be referred to the appropriate medical specialist to treat the incidentally found condition.

The known or expected risks are:

- 1) Bleeding - EUS fine needle aspiration and EUS FNB rarely (<0.01%) cause bleeding but this is not expected to be increased measurably by the one additional pass made for research purposes. The risk of bleeding will be minimized by the use of experienced gastroenterologists who will perform the EUS FNBs with Doppler assistance to identify and avoid intervening vasculature during needle puncture.
- 2) Pancreatitis - A risk of EUS-FNB is pancreatitis, which is inflammation of the pancreas that is uncommonly severe. The reported risk ranges from 0-2% in the literature. It is unknown whether increased numbers of FNB passes increases the risk of pancreatitis. The risk of pancreatitis as a complication will be minimized by the use of experienced gastroenterologists who will perform the EUS procedures.
- 3) Infection - EUS fine needle aspiration and EUS FNB rarely (<0.01%) cause infection cases but this is not expected to be increased by the one additional pass made for research purposes.
- 4) Prolongation of procedure time - Acquisition of additional specimens during EUS will extend procedure duration by no more than 5 to 10 minutes. The only risk associated with this would be additional discomfort. This risk will be minimized through the continued use of sedative and pain medications given during the procedure. As per the standard of care, vital signs including oxygen saturation, heart rate, blood pressure, and cardiac rhythm will be continuously monitored.
- 5) Confidentiality breach - Data produced and collected might be revealed to persons outside the study. This risk will be minimized through the use of a code number for the patient's name. The samples will be shared with other institutions and companies to conduct the research tests, but no information that identifies the patient will be shared.

Of note, we do not anticipate any extra risks from heparin priming of the needle, as the amount of heparin present in the needle would be a trace amount.

To further minimize research-related risk, only patient undergoing endoscopic FNB for clinical purposes will be consented for the research study.

4 ELIGIBILITY

Inclusion criteria:

- Patient must be at least 18 years old.
- Patient identified as having a possible solid pancreatic lesion on computed tomography or magnetic resonance
- Patient scheduled for EUS for sampling of pancreatic mass.

Exclusion criteria:

1. Patients with known history of coagulopathy
2. Patients with history of heparin allergy
3. Patients with evidence of vascular tumors on imaging
4. Patients with history of chronic pancreatitis
5. Pregnant patients
6. Medically unstable patients
7. Unwillingness or inability to consent for the study

Patient must be willing and able to provide written informed consent.

We anticipate that 98 patients will be seen within the University of Michigan Health System and the surrounding community for this study.

5 SUBJECT ENROLLMENT

Patients or their medical records from the Michigan Medicine health system will be used to screen for recruitment.

Patients who present for care and/or consultation to Michigan Medicine, as an inpatient or an outpatient, with known or suspected solid mass lesion will be approached for recruitment. Patients will be approached by a study team member after their initial consultation with the medical staff in a private consultation room. Patient privacy will be protected by discussing the study in the private consultation rooms available adjacent to the medical procedure unit waiting area before they are brought back to the pre-operative area.

If individuals that can be consented for this study are identified ahead of procedure date, we may attempt to call them by telephone once up to 7 days in advance to discuss the research study in an effort to save time and avoid delays on the day of procedure.

6 STUDY DESIGN AND PROCEDURES

Study setting: University of Michigan- Medical Procedure Unit

Study type: Clinical Trial

Assignment of Interventions:

Enrollment: 98 patients

Randomization: Subjects will be randomized in a 1:1 allocation ratio to the heparin group or the non-heparin control group at the time of intra-procedural decision to sample the mass. We will use restrictive block randomization to ensure balanced number of participants per group. The randomization sequence will be generated centrally from a computerized binary number generator at the University of Michigan. The treatment assignments will be in opaque sealed envelopes for allocation concealment. The study coordinator will enroll participants and will assign participants to the intervention. The randomization key will be kept under lock by the study coordinator until completion of the study period.

Blinding: The participants and the pathologist will be blinded to the group allocation. The proceduralist will not be blinded to allocation given the design of the study and for patient safety.

Interventions: all subjects will undergo EUS-FNB using linear echoendoscopes (GF-UCT180 Olympus America, Center Valley, Pa, USA). All EUS-FNB procedures will be performed by 1 of 5 experienced endosonographers ([name]). Once the site is identified, the lesion will be punctured using a 22-gauge Fork-tip needle (Sharkcore needle). The sampling technique will be at the discretion of the endoscopist (e.g. stylet vs. not stylet, suction vs. not suction, fanning technique vs. to-and-fro technique, number of strokes). A total of 3 FNB passes will be performed on every procedure. The use of rapid on-site cytopathology (ROSE) will be used at the discretion of the endoscopist and will not be mandatory for this study. The tissue specimens from each the 3 passes will be collected in 3 separate jars of 10% formalin for tissue analysis. The use of heparin flushing vs. not heparin flushing, will be based on their randomized group assignments:

- Intervention group: The FNB needle will be flushed with 1 mL of heparin (100 USP/mL) and then flushed with air. Pass 1, 2, and 3 will be collected in separate jars and sent to pathology, as per standard clinical procedures. The study will pay for the cost of utilizing and submitting extra jars to pathology so that no extra cost is incurred to the patient for participating in the study. Between passes, after tissue is extracted from the needle, the needle will be flushed with 1 mL of heparin (100 USP/mL) and flushed with air before next pass is made.
- Control group: FNB will be performed as current standard methods in the medical procedure unit without the use of heparin priming. Pass 1, 2, and 3 will be collected in separate jars and sent to pathology, as per standard clinical procedures. The study will pay for the cost of utilizing and submitting extra jars to pathology so that no extra cost is incurred to the patient for participating in the study. Between passes, after tissue is extracted from the needle, the needle will be flushed saline and or air as per current standards of care.

If proceduralist feels that it is unsafe to continue with the research protocol during the procedure (examples would include inadequate tissue acquisition in the clinical jar, or clinical instability of patient during procedure), he or she reserves the right to withdraw the patient from the protocol. For patient safety, the proceduralist will not be blinded to whether the patient was randomized to the heparin or non-heparin arm. If the proceduralist deems more than 3 passes are needed for clinical purposes, the extra passes will go into a fourth jar.

Tissue Analysis:

H&E slides from the passes 1, 2, and 3 (which will be requested from pathology) will be compared in the following manner:

- A blinded clinical pathologist will examine each slide and determine
 - Is a tissue diagnosis able to be made?
 - Is the tissue adequate quality? The pathologist will create a reference scoring system and rate specimens accordingly.
- In parallel, using the HALO® image analysis platform (Indica Labs), each slide will be digitally scanned. The number of cells present on each H&E slide (cell-based analysis), the amount of blood present on each H&E slide (area-based analysis), and the size of each biopsy will be quantified (area-based analysis).

Tracking and labelling system

Each research specimen will be given a specimen ID. A spreadsheet key matching the specimen ID to the patient name and medical record number will be kept in a password and network protected database. Only study team members will have access to the spreadsheet.

Heparin priming

This study will use heparin for needle priming. The heparin product used will be BD PosiFlush™ Pre-Filled Heparin Lock Flush Syringe, 5 mL (100 USP/mL) in a 10 mL syringe. The product will be stored in a secure location within the endoscopy unit at room temperature, as per manufacturer instructions. The product has a shelf life of 18 months and will be discarded after the expiration date. We anticipate actual exposure of patient to heparin to be minimal, as after heparin flushing, needles will be air-flushed before proceeding with the next pass. We do not anticipate any adverse events from heparin priming of the needle.

Saline Flush

While there is a saline-only PosiFlush, the hospital changes its supplier of saline flushes depending on cost. Therefore, because use of saline for flushing is the routine standard of care, we will not be using specialized research PosiFlush saline syringes and instead will be using the available supply our unit keeps on stock

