9 QUALITY CONTROL AND QUALITY ASSURANCE

Sample collection and processing will be conducted by highly trained proceduralists and staff.

Tissue scoring will be performed by blinded clinical pathologist [name], PhD.

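### The plan blinds the pathologist to arm but does not provide for masking pass number, so the within-arm tissue-score comparisons across passes are open to reader expectation

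*Combined protocol and SAP*

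**What the plan says.** Section 6 (Blinding) states what the pathologist is masked to: "The participants and the pathologist will be blinded to the group allocation". Later references repeat the word without widening it. The tissue analysis text in Section 6 reads "A blinded clinical pathologist will examine each slide and determine", and Section 9 reads "Tissue scoring will be performed by blinded clinical pathologist".

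Pass number is a study factor in its own right. The hypothesis in Section 2 is that "the tissue quality of EUS-FNB specimens of pancreatic masses decreases with increasing pass number due to blood contamination", and a secondary objective is "Determine whether increasing number of FNB passes affects tissue quality, block contamination, and histologic yield". A further secondary objective is the incremental diagnostic yield of a second or third pass.

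On handling, Section 6 says "The tissue specimens from each the 3 passes will be collected in 3 separate jars of 10% formalin for tissue analysis", and for both arms "Pass 1, 2, and 3 will be collected in separate jars and sent to pathology, as per standard clinical procedures". The H&E slides are then requested back from pathology for the study reading. The same pathologist devises the scoring system and applies it; the scale is not given. Section 6 also assigns each research specimen an ID, with a key described as linking that ID to patient name and record number.

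Section 8 plans a Pearson chi-squared test of tissue score across the three passes, separately in each arm, and between arms at each pass.

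**The concern.** When two arms are compared at the same pass, masking the arm protects the reading. When passes are compared within an arm, the exposure is the pass, and masking the arm gives no protection. The plan keeps the passes physically separate through to pathology, states which direction it expects, and has one reader apply a judgement scale of that reader's own making. It does not say that the reader is kept from knowing which pass a slide came from, or that one patient's three slides are not read side by side.

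Section 1 says the results will guide how many passes are needed and how passes are divided among applications. An apparent decline in score that came from expectation would feed into that advice, and once slides have been read without masking no analysis can separate the two explanations. Section 1 also criticises the earlier crossover trial for a measurement method prone to investigator bias, so the same standard fairly applies to the score by pass.

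**Working it through.** **Step 1: the text.** Only the Blinding paragraph of Section 6 names an object of masking, and that object is group allocation. Sections 3, 8 and 9 and the tissue analysis text of Section 6 use the word without an object. Nothing describes recoding of slides, reading order or the content of slide labels. The specimen ID could hide pass number, but its only described function is to link to patient identity.

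**Step 2: which analyses are exposed.**
- Tissue score across passes, heparin arm and control arm (two tests in Section 8): exposed.
- Whether a tissue diagnosis can be made, as used for incremental yield by pass: exposed. Section 8 lists no test for it.
- Tissue score between arms at the same pass: largely protected, because an expectation about pass would act on both arms alike.
- Cell number, blood area and tissue area: quantified by image software, so much less exposed. These include the primary outcomes in Section 8 (cellularity and blood contamination) and its secondary outcomes on successive passes.

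**Step 3: the sample size used below.** Section 8 gives SD 5 mm², difference 3 mm², type I error 0.05 and power 80%. Taking the test as two-sided, n per arm = 2 × (1.960 + 0.842)² × 5² / 3² = 43.6, so 44. Allowing for dropout, 88 / 0.90 = 97.8, so 98. The plan's figures reproduce, and nothing in this point changes them.

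**Step 4: size of the effect on the planned test.** The following are assumptions and do not come from the documents: a binary adequate/inadequate score, 80% adequacy at every pass, no true pass effect, and a reader who downgrades a fraction d of adequate pass-3 slides. Then p₁ = p₂ = 0.80 and p₃ = 0.80 × (1 − d).

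With independent passes, the 2×3 Pearson statistic (2 df, critical value 5.991) has noncentrality λ = n Σ(pₖ − p̄)² / [p̄(1 − p̄)], with n = 44. For d = 10%, p̄ = 0.7733, Σ(pₖ − p̄)² = 0.004267, and λ = 44 × 0.004267 / (0.7733 × 0.2267) = 1.07.

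With a within-patient correlation of 0.3 between the binary scores, the rejection rates come from simulation of the same test.

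| d | p₃ | λ | Rejection, independent passes | Rejection, correlation 0.3 |
|---|---|---|---|---|
| 0% | 0.80 | 0 | about 5% | about 1.5% |
| 5% | 0.76 | 0.28 | about 7% | about 3% |
| 10% | 0.72 | 1.07 | about 14% | about 9% |
| 15% | 0.68 | 2.32 | about 25% | about 21% |

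Check on the first row: under equal correlation ρ the statistic behaves approximately as (1 − ρ) times a chi-squared on 2 df, so rejection is exp[−5.991 / (2 × 0.7)] = exp(−4.28), about 1.4%. The planned test ignores the pairing and is therefore conservative before any bias enters.

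**Step 5: a different bias pattern.** If expectation lowers adequacy at each successive pass (80%, then 80% − s, then 80% − 2s), independent passes give about 7.5%, 15% and 43% for s of 2.5, 5 and 10 points. For s = 5 points, λ = 44 × 0.005 / (0.75 × 0.25) = 1.17. Over base adequacy of 70% to 90%, the ranges are about 7–9%, 13–20% and 38–55%.

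**The case against.** The strongest reply is that the document is silent and does not say that the reader sees the pass. Slides are requested from pathology and may carry the specimen ID, several sections say blinded without limiting it to arm, and the sponsor may already intend full masking. That stands in part: it sets the kind of finding this is. It does not close the gap, because the only sentence that defines the masking stops at group allocation.

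A reader might infer that slide labels follow pass order and that the pathologist knows the hypothesis. Neither is documented. A reader might also infer that the trial's main conclusions are at risk. They are largely not: the primary outcomes are between-arm and software-measured, and the pass hypothesis has a parallel software-based answer.

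The size also needs restraint. A paired test of pass 1 against pass 3 with both arms pooled (88 patients) would reject about 11% or 27% of the time at 5% or 10% downgrading, but the plan contains no such test. With the planned test and correlation 0.3, 5% downgrading leaves rejection below the nominal 5%. This part of the objection stands in full. Against it, 10 to 15% downgrading takes rejection to about 9 to 21% even so, from a starting point of about 1.5%.

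The study also calls itself a pilot. That lowers the stakes, but the safeguard costs little.

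**Conclusion.** The point holds in limited form. The plan masks the pathologist to arm and does not provide for masking pass number or randomising reading order, although pass number is a directional hypothesis tested on a subjective score. The exposure is confined to the two within-arm tissue-score comparisons and the incremental diagnostic yield by pass. The documents do not support a claim that the reader is in fact unblinded to pass, or that the primary outcomes are compromised.

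The size depends on how much a reader would downgrade later passes, which is unknown. It ranges from negligible at 5% downgrading of pass 3 to about 21–25% false rejection at 15%, and is larger if expectation acts at every successive pass and passes are independent. Adequacy, correlation, downgrading and the binary form of the score are all assumed. This is a worthwhile, cheap improvement and does not threaten the trial's validity as a whole.

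**What to change.** Amend the Blinding paragraph of Section 6, before any slide is read, to say that:
- the pathologist is blinded to arm, patient and pass number;
- slides carry a random specimen ID that does not encode pass order, with any original label covered or replaced;
- slides are read in random order across patients, passes and arms;
- the key is opened only after scores are locked.

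Section 3 already commits to notifying a patient if the study reading finds a malignancy that the clinical passes missed. The wording should let the key holder, not the reader, trace that specimen, so that masking does not obstruct the commitment.

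The cost is recoding or covering labels on about 98 × 3 = 294 slides, assuming one slide per pass (the document does not give the number). Specimen IDs are already planned. No extra reader is needed and the sample size does not change. If this masking is already intended, the amendment simply records it.

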7 DATA COLLECTION AND MANAGEMENT PROCEDURES

Collection of medical record data for this study will include the following:

Initial collection:

- Patient demographic data:
 - Age
 - Sex
 - BMI
 - Pack Years
 - Presence of Diabetes, Type 1 or 2
 - Alcohol use
 - History of Pancreatitis
 - History of IPMN (intraductal papillary mucinous neoplasms)
 - Prior Cancer History

Follow up collection (approximately 4 weeks post-procedure):

- Was patient reached for follow-up?
- Did patient develop post-procedural complications?
- Did patient need interventions for post-procedural complications?
- Was hospital admission required for post-procedure complication?
- Did patient require repeated EUS for sampling?
- Age Patient demographic data:

Chart review at end of study (after 98 patients collected)

- Development of new pancreatic disease other than cancer
- Overall survival (date of death)
- Cancer Stage
 - If resectable, did patient receive surgery?
 - If yes
 - What surgery (distal pancreatectomy vs Whipple?)

- Final surgical staging
- Tumor grade
- Chemotherapy treatment
 - Palliative, neoadjuvant, or adjuvant chemo
 - Regimen (FOLFIRINOX, Gemcitabine/abraxane, Gemcitabine/cisplatin)
- ECOG score
- Final Diagnosis

. Data will be pulled from patient's medical charts via both DataDirect and chart review. Regarding data management we will seek assistance with the MICHR database development service. The study team may collect data from each research participant for up to 5 years from when they were consented. This data will be stripped of patient name and stored using REDCap; only the study team members have access to this database. On the database, patient identity will not be discernable to the casual observer. As indicated in section 6, separate from this, a spreadsheet key matching the specimen ID to the patient name and medical record number will be kept in a password and network protected database. Only study team members will have access to this spreadsheet.

SCHEDULE OF EVENTS8 DATA ANALYSIS

Primary Outcomes

- Heparin priming increases cellularity captured in fine needle biopsies
- Heparin priming decrease blood contamination in fine needle biopsies

Secondary Outcomes

- Successive fine needle biopsy passes result in more blood contamination
- Successive fine needle biopsy passes have lower cellular yield
- Successive fine needle biopsy passes have more blood contamination
- Need for repeated procedure (at U of M)

Exploratory Outcomes

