- Identify correlations in patient metadata (i.e. tumor grade, cancer stage) and tissue quality, cellular yield, and blood contamination

Tissue analysis:

H&E slides from the pass 1, 2, and 3 (which will be requested from pathology) will be compared in the following manner:

- A blinded clinical pathologist will examine each slide and determine
 - Is a tissue diagnosis able to be made?
 - Is the tissue adequate quality (pathologist will make a reference scoring system and rank specimens accordingly)

In parallel, using image processing software, the number of cells present on each H&E slide will be quantified, the amount of blood present on each H&E slide will be quantified by area quantification, and the tissue yield on each H&E slide will be quantified by area quantification.

Statistical Comparisons using image analysis:

The student *t* test will be utilized to assess if there is a significant difference in the following:

- Blood contamination area between passes 1, 2, and 3 in the heparin group
- Blood contamination area between passes 1, 2, and 3 in the non-heparin group
- Blood contamination area in pass 1 between the heparin group and non-heparin group
- Blood contamination area in pass 2 between the heparin group and non-heparin group
- Blood contamination area in pass 3 between the heparin group and non-heparin group
- Tissue area between passes 1, 2, and 3 in the heparin group
- Tissue area between passes 1, 2, and 3 in the non-heparin group
- Tissue area in pass 1 between the heparin group and non-heparin group
- Tissue area in pass 2 between the heparin group and non-heparin group
- Tissue area in pass 3 between the heparin group and non-heparin group
- Cell number between passes 1, 2, and 3 in the heparin group
- Cell number between passes 1, 2, and 3 in the non-heparin group
- Cell number in pass 1 between the heparin group and non-heparin group
- Cell number in pass 2 between the heparin group and non-heparin group
- Cell number in pass 3 between the heparin group and non-heparin group

Statistical Comparisons using pathologist scoring:

The Pearson's Chi-squared test will be utilized to determine if there is a significant difference in the following:

- Tissue score between passes 1, 2, and 3 in the heparin group
- Tissue score between passes 1, 2, and 3 in the non-heparin group
- Tissue score in pass 1 between the heparin and non-heparin group
- Tissue score in pass 2 between the heparin and non-heparin group

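### Five endosonographers sample with discretionary technique, but the arm comparisons are unadjusted t tests: valid and powered as planned, yet a possible gain in precision is forgone

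*Combined protocol and SAP*

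**What the plan says.** Section 6 (Interventions): "All EUS-FNB procedures will be performed by 1 of 5 experienced endosonographers". It adds that "The sampling technique will be at the discretion of the endoscopist", giving stylet use, suction, needle movement and stroke count as examples.

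Section 6 (Randomization): allocation is 1:1, and "We will use restrictive block randomization to ensure balanced number of participants per group". No stratification factor is named.

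Section 8 (comparisons using image analysis): the Student t "test will be utilized to assess if there is a significant difference in the following", followed by a list for blood area, tissue area and cell number. The between-arm entries are made pass by pass, for example "Tissue area in pass 1 between the heparin group and non-heparin group". No covariate or operator term appears there or in Section 10. Patient and tumour characteristics enter only as an exploratory outcome: "Identify correlations in patient metadata (i.e. tumor grade, cancer stage) and tissue quality, cellular yield, and blood contamination".

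Section 7 lists the items to be collected. Neither the endoscopist nor lesion size is among them.

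Section 1 criticises the earlier crossover trial for relying on a single endoscopist, so using several operators answers a weakness that the protocol itself identifies.

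**The concern.** The technique choices left to the operator bear on how tissue and blood enter the needle, and tissue and blood are what the trial measures. If operators differ systematically, that variation sits in the error term of every between-arm t test, although the operator is known before the first pass and could be adjusted for.

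What is at stake is precision. The planned sample gives about 80% power with little margin if dropout reaches the planned 10%. An adjusted model would narrow the confidence interval to the extent that operator, or another baseline factor, explains the outcome. Because endoscopist is not on the data list, later adjustment might mean going back to the charts, and a covariate chosen after the results are seen would carry less weight.

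**Working it through.** **Inputs.** From Section 8: difference 3 mm², SD 5 mm², 44 evaluable per arm, type I error 0.05, power 80%, 10% dropout, 98 recruited. From Section 6: five operators. R² is not in the documents, so the values below are assumptions.

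**1. The plan's own figure.** n per arm = 2 × SD² × (1.960 + 0.842)² / difference² = 2 × 25 × 7.849 / 9 = 43.6, rounded up to 44. Total 88 / 0.9 = 97.8, so 98. Both figures reproduce with a two-sided test; a one-sided test would need 35 per arm.

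**2. Unadjusted power.** Standard error = 5 × √(2/44) = 1.066 mm². Noncentrality = 3 / 1.066 = 2.814. With 86 degrees of freedom, power is 79.5% (80.4% by the normal approximation). If all 49 per arm are evaluable it is 83.6%.

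**3. Adjusted power.** Five added terms: four for endoscopist and one for a baseline covariate such as lesion size.
- Residual SD = 5 × √(1 − R²).
- Degrees of freedom = 86 − 5 = 81.
- Noncentrality = 3 / (residual SD × √(2/44)) if the covariates happen to be balanced between arms.
- Conservative case: multiply by √(1 − 5/87). Here 5/87 is the share of the arm indicator's variance that five unrelated terms explain by chance, on average, in 88 patients.

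| Assumed R² | Residual SD (mm²) | Noncentrality, conservative to balanced | Power |
|---|---|---|---|
| 0 | 5.00 | 2.732 to 2.814 | 77.0-79.4% |
| 0.05 | 4.87 | 2.803 to 2.887 | 79.1-81.4% |
| 0.10 | 4.74 | 2.880 to 2.967 | 81.2-83.4% |
| 0.20 | 4.47 | 3.055 to 3.146 | 85.5-87.5% |

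Against 79.5% unadjusted, the worst-case cost at R² = 0 is 79.5 − 77.0 = 2.5 points. Conservative break-even is R² of about 5.9%. With endoscopist alone (four terms, factor 1 − 4/87), power is 77.5-79.4% at R² = 0, a cost of up to 2.0 points, and conservative break-even is about 4.7%.

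**4. Chance imbalance between operators.** Simulating 88 patients, 44 per arm, with equal caseloads for the five operators (assumed) and no stratification, at least one operator's arm counts differ by 6 or more in about 52% of trials and by 8 or more in about 21%. If operators explain 10% of the variance (assumed), the resulting shift in the estimate has an SD of about 0.30 mm², against the total standard error of 1.07 mm².

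**5. Reach of the figures.** The 3 mm² and 5 mm² concern total tissue area. The Section 8 t tests are per pass, and the primary outcomes listed there are cellularity and blood contamination. The documents give no SD or target difference for those, so steps 2 to 4 do not transfer to them.

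**The case against.** The strongest reply is that nothing is broken. Randomisation makes the unadjusted t test valid, the sample size was computed for that test, and the figure reproduces. Any gain from adjustment rests on an R² that nobody has stated. Technique may also vary between one operator's own procedures, which an operator term would not absorb, and the study describes itself as a pilot. All of this stands, and it makes the point an improvement rather than a correction.

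Four stronger readings are tempting, and the documents support none of them:

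- **That planned power is lost.** This would follow only if the SD of 5 mm² excluded operator and lesion variation. A true total SD of 5.27 or 5.59 mm² (5 / √0.9 or 5 / √0.8) would give about 76% or 71% by the normal approximation. Section 8 takes the SD from a previous study and does not say that it was adjusted. If it is the total between-patient SD, that variation is already counted.
- **That operator imbalance biases the result.** Imbalance is likely in any one trial, but it is random, and the t test's standard error already covers it. It is the same lost precision seen from another side, not a second problem.
- **That lesion size is known to limit yield.** No section says so, and none quantifies variation between operators.
- **That the trial has no reserve.** Power is 83.6% if all 98 are evaluable.

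What survives is narrower: operator is a design feature fixed before sampling, the plan itself leaves technique to the operator, and neither the allocation nor the analysis uses that information.

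**Conclusion.** The point holds as a cheap improvement. The unadjusted between-arm tests are valid and meet the planned power of about 80%, but the plan passes over a possible gain in precision. For total tissue area at 44 per arm, the gain over 79.5% would be roughly 2 to 4 points at R² = 0.10 and 6 to 8 points at R² = 0.20. If the factors explain nothing, the change ranges from a negligible loss to one of about 2.5 points.

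This rests on the plan's own difference and SD, on SD 5 mm² being the total between-patient SD, and on assumed values of R². The existence of five operators and the absence of any operator term are documented; the size of any operator effect is not.

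**What to change.** Before any arm-level data are seen:

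1. In Section 8, prespecify a linear model with arm and endoscopist (as a factor) for the between-arm comparisons of tissue area, blood area and cell number. Keep the unadjusted t test as a sensitivity analysis, and state that the adjusted estimate is the one to be reported first.
2. In Section 7, add the endoscopist to the data list.
3. Optionally, record lesion size before sampling and name it as a baseline covariate. Its effect on yield should be described as an assumption.

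The cost is a few sentences in the analysis section and one data field, or two with lesion size. Sample size and study procedures do not change. The statistical price is 4 to 5 degrees of freedom and up to about 2 to 2.5 points of power if the factors explain nothing. On the conservative calculation the model pays for itself once they explain about 5 to 6% of the variance.
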